10.3.1.1. RECIST

Disease response will be assessed according to the RECIST criteria v1.1 ([Appendix 1](#)).

10.3.1.2. iRECIST

Antitumor response based on assessment of changes in tumor burden will be assessed by iRECIST ([Appendix 2](#)). The RECIST 1.1 definitions will be used to determine “immune” response: PFS and ORR.

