APPENDIX 1. RECIST VERSION 1.1

(Modified from [Eisenhauer 2009](#))

All patients will have their BEST RESPONSE on study classified as outlined below:

Complete Response (CR)

Disappearance of all target lesions. Any pathological lymph nodes (whether target or non target) must have reduction in the short axis to <10mm.

Partial Response (PR)

At least a 30% decrease in the sum of diameters of target lesions, taking as reference the baseline sum diameters.

Stable Disease (SD)

Steady state of disease. Neither sufficient shrinkage to qualify for PR nor sufficient increase to qualify for PD.

Progressive Disease (PD)

At least a 20% increase in the sum of diameters of measured lesions taking as references the smallest sum of diameters recorded since the treatment started. In addition to the relative increase of 20%, the sum must also demonstrate an absolute increase of at least 5 mm. Appearance of one or more new lesions will also constitute progressive disease.

Response Duration

Response duration will be measured from the time measurement criteria for CR/PR (whichever is first recorded) are first met until the first date that recurrent or progressive disease is objectively documented, taking as reference the smallest measurements recorded since the treatment started.

Stable Disease Duration

Stable disease duration will be measured from the time of start of therapy until the criteria for progression are met, taking as reference the smallest measurements recorded since the treatment started.

Evaluation of Best Overall Response – Patient with Target (\pm non-target) disease

Target lesions	Non-Target lesions	New Lesions	Overall response
CR	CR	No	CR
CR	Non-CR-Non-PD	No	PR
CR	NE	No	PR
PR	Non-PD/or not all evaluated	No	PR
SD	Non-PD/or not all evaluated	No	SD
Not all evaluated	Non-PD	No	NE

Target lesions	Non-Target lesions	New Lesions	Overall response
PD	Any	Yes or No	PD
Any	PD	Yes or No	PD
Any	Any	Yes	PD

CR: complete response; NE: non-evaluable; PD: progressive disease; PR: partial response; SD: stable disease.

Evaluation of Best Overall Response – Patient with Non-Target Disease

Non-Target lesions	New Lesions	Overall response
CR	No	CR
Non-CR-Non-PD	No	Non-CR/Non-PD ¹
Not all evaluated	No	NE
Unequivocal PD	Yes or No	PD
Any	Yes	PD

CR: complete response; NE: non-evaluable; PD: progressive disease; PR: partial response.

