Note: Patients with a global deterioration of health status requiring discontinuation of treatment without objective evidence of disease progression at that time should be reported as “*symptomatic deterioration*”. Every effort should be made to document the objective progression even after discontinuation of treatment.

Method of Measurement

The same method of assessment and the same technique should be used to characterize each identified and reported lesion at baseline and during follow-up.

Clinical Lesions

Clinical lesions will only be considered measurable when they are superficial (e.g., skin nodules, palpable lymph nodes). For the case of skin lesions, documentation by color photography including a ruler to estimate the size of the lesion is recommended.

CT, MRI

CT and MRI might be the best currently available and reproducible methods to measure target lesions selected for response assessment. Conventional CT and MRI should be performed with cuts of 10 mm or less in slice thickness contiguously. Spiral CT should be performed using a 5 mm contiguous reconstruction algorithm. This applies to the chest, abdomen and pelvis. Head & neck and extremities usually require specific protocols.

Cytology, Histology

These techniques can be used to differentiate between PR and CR in rare cases (for example, residual lesions in tumor types such as germ cell tumors, where known residual benign tumors can remain). The cytological confirmation of the neoplastic origin of any effusion that appears or worsens during treatment when the measurable tumor has met criteria for response or stable disease

is mandatory to differentiate between response or stable disease (an effusion may be an adverse drug reaction of the treatment) and PD.

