Immune best overall response (iBOR) is determined as with RECIST 1.1 if there is no iUPD. In the case of iUPD, a subsequent iBOR of iSD, iPR, or iCR is still possible if the overall RECIST 1.1 criteria are met, provided that the criteria for iCPD (that is, disease progression at the assessment following iUPD) are not met. The duration of iCR and iPR is from the timepoint when criteria for iCR or iPR are first met; the duration of iSD is calculated from baseline.

For immune progression-free survival (iPFS), the event date should be the first date at which progression criteria are met (ie, the date of iUPD) provided that iCPD is confirmed at the next assessment. The date of an iUPD that is disregarded due to iSD, iPR, or iCR at the next visit should not be used as the progression event date. [Table 13](#) illustrates comparisons between RECIST 1.1 and iRECIST, and [Table 14](#) provides guidance for assigning timepoint response without or with previous iUPD.

Comparison of RECIST 1.1 and iRECIST

	RECIST 1.1	iRECIST
Definitions of measurable and non-measurable disease; numbers and site of target disease	Measurable lesions are ≥ 10 mm in diameter (≥ 15 mm for nodal lesions); maximum of 5 lesions (2 per organ); all other disease is considered non-target (must be ≥ 10 mm in short axis for nodal disease)	No change from RECIST 1.1; however, new lesions are assessed as per RECIST 1.1 but are recorded separately on the eCRF (but not included in the sum of lesions for target lesions identified at baseline)
Complete response, partial response, or stable disease	Cannot have met criteria for progression before complete response, partial response, or stable disease	Can have had iUPD (one or more instances), but not iCPD, before iCR, iPR, or iSD
Confirmation of complete response or partial response	Required for non-randomized trials	As per RECIST 1.1
Confirmation of stable disease	Not required	As per RECIST 1.1
New lesions	Result in progression; recorded but not measured	Result in iUPD, but iCPD is assigned on the basis of this category ONLY if at the next assessment additional new lesions appear or an increase in size of new lesions is seen (≥ 5 mm for sum of new lesion target or any increase in new lesion non-target); the appearance of new lesions when none have previously been recorded, can also confirm iCPD.
Confirmation of progression	Not required	Required

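### Appendix 1 allows 10 mm slices for conventional CT and MRI but does not tie the 10 mm measurable-lesion minimum to slice thickness, so a sole small target can occasionally cross the PR threshold by slice placement alone

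*Protocol*

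**What the plan says.** Section 10.3.1.1 of the protocol sends the reader to Appendix 1: "Disease response will be assessed according to the RECIST criteria v1.1". Section 10.3.1 accepts either CT or MRI and does not require spiral CT.

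For chest, abdomen and pelvis, Appendix 1 sets two slice rules in consecutive sentences:

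- "Conventional CT and MRI should be performed with cuts of 10 mm or less in slice thickness contiguously"
- For spiral CT, the next sentence halves that figure and asks for reconstruction at 5 mm.

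The size minimum for CT and MRI lesions appears only in the Appendix 2 comparison table: "Measurable lesions are ≥ 10 mm in diameter (≥ 15 mm for nodal lesions", with a "maximum of 5 lesions (2 per organ". Inclusion criterion 4 asks for measurable disease under RECIST v1.1 and adds no slice condition.

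Appendix 1 defines PR as "At least a 30% decrease in the sum of diameters of target lesions, taking as reference the baseline sum diameters". On confirmation of CR or PR, the RECIST 1.1 column of the Appendix 2 table reads "Required for non-randomized trials". The ORR definitions (Protocol Sections 5 and 12.4.1.1; SAP Sections 1.3.1 and 4.2.1) do not repeat that requirement.

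**The concern.** A lesion about as thick as one slice may lie within a single slice or be split between two. When it is split, each slice averages lesion with background, and the apparent diameter shrinks although the lesion has not changed. Slice position relative to the lesion is not controlled from scan to scan, so an unchanged small target can read large at baseline and small later.

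The protocol permits slices as thick as the smallest measurable lesion for conventional CT and for all MRI of the trunk, yet asks for half that thickness on spiral CT.

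The primary endpoint is ORR, read by the investigator, with 20 patients planned per arm (Section 6.1). One wrongly scored PR would move an arm's ORR by 1/20 = 5 percentage points. The same measurements feed PD, DOR, PFS and the measurable-disease criterion.

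**Working it through.** The documents give no measurement-error figure to reproduce, so this is a geometric check.

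**Inputs from the protocol.** Slice thickness T = 10 mm (conventional CT, MRI) or 5 mm (spiral CT), Appendix 1. Minimum measurable size 10 mm, or 15 mm for nodes, Appendix 2. PR is a fall of at least 30% in the sum; PD is a rise of at least 20% and at least 5 mm over the smallest sum, Appendix 1.

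**Assumptions, not in the documents.** The lesion is an unchanged sphere of diameter D. Slices are contiguous. The distance o from the lesion centre to the middle of the nearest slice is uniform on 0 to T/2, independently at each scan. The edge is drawn where the lesion fills half the slice. Every target reads at least 10 mm at baseline.

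**Formula.** Reading = √(D² − 4m²), where m is the larger of o and T/4. The highest reading is √(D² − T²/4); the lowest is √(D² − T²).

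**Who is exposed at T = 10 mm.**
- To qualify at baseline: √(D² − 25) ≥ 10, so D ≥ √125 = 11.18 mm.
- For a 30% fall to be possible: √(D² − 100) ≤ 0.7·√(D² − 25), so 0.51·D² ≤ 87.75 and D ≤ 13.12 mm.

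The exposed range is therefore about 11 to 13 mm.

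**Example, D = 12 mm.** Readings run from √44 = 6.63 to √119 = 10.91 mm. From a baseline of 10.91, PR needs 7.64 or less: 4o² ≥ 144 − 58.31 = 85.69, so o ≥ 4.63 and the chance is (5 − 4.63)/5 = 7.4%. From a baseline of 10.0, PR needs 7.0 or less: 4o² ≥ 95, so o ≥ 4.87 and the chance is 2.5%. Averaged over qualifying baselines (simulation), the chance is 7%.

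**Sole target, T = 10 mm.**

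| D (mm) | Highest | Lowest | Largest fall | False PR, one scan | False PR, two scans |
|---|---|---|---|---|---|
| 11.2 | 10.02 | 5.04 | 49.7% | 13% | 2% |
| 11.5 | 10.36 | 5.68 | 45.2% | 11% | 1.1% |
| 12.0 | 10.91 | 6.63 | 39.2% | 7% | 0.5% |
| 12.5 | 11.46 | 7.50 | 34.5% | 3% | 0.1% |

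**Sum of lesions.** One-scan false PR is about 1% for two 12 mm targets and about 0.2% for three.

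**T = 5 mm.** A 12 mm lesion reads √119 = 10.91 to √137.75 = 11.74 mm. The chance of a false PR is 0% at every size in the table.

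**False PD at T = 10 mm.** For one target, the whole span of readings is 4.98 mm at 11.2, 4.68 at 11.5 and 4.27 at 12.0 mm. This is under the 5 mm required, so a single target cannot give a false PD in this model. With two or three targets of 12 to 13 mm, a low follow-up reading can set the smallest sum and the next scan can then exceed it by 5 mm; the chance is about 1 to 4%.

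**Other ways of reading the edge.**
- Diameter taken at the slice mid-plane, 2·√((D/2)² − o²): a 30% fall is possible up to D = 10/√0.51 = 14.0 mm. A sole 12 mm target has a 10.4% chance on one scan and 1.2% on two; a sole 10 mm target has 28.6% and 8.2%. The span at 12 mm is 12 − 6.63 = 5.37 mm, so the single-target PD result above belongs to the half-contrast model. On 5 mm slices the largest fall for a 10 mm lesion is 13.4%.
- Edge at half of the lesion's own peak signal: a 10 mm lesion on 10 mm slices varies by only 8.1%.
- For a 15 mm node on 10 mm slices, the largest mid-plane fall is 25.5%, short of 30%.

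**The case against.** The strongest reply is that several conditions must coincide. The patient needs a sole non-nodal target in a band about 2 mm wide, imaged on slices near 10 mm. The 10 mm figure is a ceiling, nothing in the documents shows that any site uses it, and the next sentence of Appendix 1 sets 5 mm for spiral CT. PR is judged on a sum of up to five lesions. Confirmation, if applied, removes most of what remains. Appendix 1 also asks for an unchanged measurement technique for each lesion, and Section 10.3.1 for an unchanged modality. Inclusion criterion 4 relies on RECIST v1.1 itself, whose full text is not before us and may carry its own slice condition.

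Most of this stands and limits the point to the size given here. Three parts do not dispose of it. Constant technique does not fix where the slice boundaries fall. Confirmation is stated only in a table comparing RECIST with iRECIST, not in the ORR definitions or in the Appendix 1 PR rule. And whatever the parent guideline says, the protocol's own text permits the combination.

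A reader might infer that ORR is biased upward, or that each arm should expect an error of 5 points. The documents do not support either. They give no mix of scanners or lesion sizes and no edge-reading rule, and the error also works in reverse: a baseline that reads too small can hide a true response.

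**Conclusion.** The point holds in a narrow form. Appendix 1 permits slices as thick as the smallest measurable lesion, and no rule connects the two. Under the half-contrast sphere model, an unchanged sole non-nodal target of about 11 to 13 mm on 10 mm slices can read at least 30% smaller on one scan: about 3 to 13% for 11.2 to 12.5 mm, falling to zero by 13.1 mm. With confirmation on a second scan this is about 0 to 2%. False response from this cause is absent on 5 mm spiral CT, for nodes of 15 mm or more, and for lesions above about 14 mm under either model that produces it.

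These figures rest on spherical lesions, random slice position and a fixed edge rule. Across the edge rules tried, the placement effect for a 10 mm lesion ranges from 8% to 100% of its diameter. The net effect on ORR cannot be estimated. This is an inexpensive tightening of the measurement rule, not a defect that undermines the primary analysis.

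**What to change.** In Appendix 1, replace the 10 mm allowance with wording such as: CT and MRI are acquired or reconstructed at a slice thickness of 5 mm or less, with the same thickness at every visit; where slices are thicker, a non-nodal lesion is measurable only if its longest diameter is at least twice the slice thickness. Refer to this rule in inclusion criterion 4.

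This extends the protocol's own spiral-CT figure. At the fallback limit of 20 mm on 10 mm slices, the lowest mid-plane reading is 17.32 mm, a largest fall of 13.4%, the same as for a 10 mm lesion on 5 mm slices. Neither comes near 30%.

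The cost is one sentence in Appendix 1 and a cross-reference. The downside is that a patient whose only lesion is small and imaged with thick slices needs a thinner reconstruction or is not eligible. Stating in the ORR definition whether confirmation is required is a separate clarification, which would reduce the remaining risk further.

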APPENDIX 2. iRECIST

(Modified from [Seymour 2017](#))

A systematic modification of RECIST 1.1 was undertaken by the RECIST Working Group to address observations of the patterns of response of tumors to immune-modulating agents, which resemble tumor flare and have been termed pseudoprogression. Some patients who experience these increases in tumor measurement after immunotherapy go on to have late, but deep and durable responses. Therefore, a data-driven method was developed for consistently measuring tumor response to immune-based therapeutics.

RECIST 1.1 is still used to define measurability and for management of bone lesions, cystic lesions, and lesions with previous local treatment. The method of tumor measurement (CT/MRI preferred) is also unchanged. The main modification is the concept of resetting the dimensions against which following assessments are measured if RECIST 1.1 progression is followed by tumor shrinkage.

The assessment of timepoint response is unchanged from RECIST 1.1; that is, the method of assessment of target and non-target lesions, lymph nodes, lesions that become too small to measure, lesions that split or coalesce, and the definitions of CR, PR, SD, and PD. The RECIST 1.1 definitions are used to determine “immune” response: immune complete response (iCR), immune partial response (iPR), immune stable disease (iSD), immune unconfirmed progressive disease (iUPD), and immune confirmed progressive disease (iCPD).

The difference primarily lies in the ability to assign responses of iCR, iPR, and iSD after iUPD has been documented, as long as progression is not confirmed at the next assessment, resulting in iCPD. If iUPD is not confirmed at the following assessment (per RECIST 1.1 – that is, increase in size or number of lesions), the response for that timepoint is defined by the RECIST 1.1 guidelines for response. If tumor shrinkage occurs (compared with baseline) meeting the criteria of iCR, iPR, or iSD, then iUPD must occur again (compared with nadir values) and be confirmed (by further growth) for iCPD to be assigned. If there is no change in tumor number or size from the iUPD, the timepoint response would again be iUPD. The assessment of iUPD can be made multiple times, with iCR, iPR, or iSD occurring afterward as long as iCPD is not confirmed at the next assessment.

Immune best overall response (iBOR) is determined as with RECIST 1.1 if there is no iUPD. In the case of iUPD, a subsequent iBOR of iSD, iPR, or iCR is still possible if the overall RECIST 1.1 criteria are met, provided that the criteria for iCPD (that is, disease progression at the assessment following iUPD) are not met. The duration of iCR and iPR is from the timepoint when criteria for iCR or iPR are first met; the duration of iSD is calculated from baseline.

For immune progression-free survival (iPFS), the event date should be the first date at which progression criteria are met (ie, the date of iUPD) provided that iCPD is confirmed at the next assessment. The date of an iUPD that is disregarded due to iSD, iPR, or iCR at the next visit should not be used as the progression event date. [Table 13](#) illustrates comparisons between RECIST 1.1 and iRECIST, and [Table 14](#) provides guidance for assigning timepoint response without or with previous iUPD.

Comparison of RECIST 1.1 and iRECIST

	RECIST 1.1	iRECIST
Definitions of measurable and non-measurable disease; numbers and site of target disease	Measurable lesions are ≥ 10 mm in diameter (≥ 15 mm for nodal lesions); maximum of 5 lesions (2 per organ); all other disease is considered non-target (must be ≥ 10 mm in short axis for nodal disease)	No change from RECIST 1.1; however, new lesions are assessed as per RECIST 1.1 but are recorded separately on the eCRF (but not included in the sum of lesions for target lesions identified at baseline)
Complete response, partial response, or stable disease	Cannot have met criteria for progression before complete response, partial response, or stable disease	Can have had iUPD (one or more instances), but not iCPD, before iCR, iPR, or iSD
Confirmation of complete response or partial response	Required for non-randomized trials	As per RECIST 1.1
Confirmation of stable disease	Not required	As per RECIST 1.1
New lesions	Result in progression; recorded but not measured	Result in iUPD, but iCPD is assigned on the basis of this category ONLY if at the next assessment additional new lesions appear or an increase in size of new lesions is seen (≥ 5 mm for sum of new lesion target or any increase in new lesion non-target); the appearance of new lesions when none have previously been recorded, can also confirm iCPD.
Confirmation of progression	Not required	Required
Consideration of clinical status	Not included in assessment	Clinical stability is considered when deciding whether treatment is continued after iUPD

“i” indicates immune responses assigned using iRECIST.

Abbreviations: iCPD = confirmed progression; iCR = complete response; iPR = partial response; RECIST = Response Evaluation Criteria in Solid Tumors; iSD = stable disease; iUPD = unconfirmed progression.

Assignment of Timepoint Response Using iRECIST

	Timepoint Response with No Previous iUPD in Any Category	Timepoint Response with Previous iUPD in Any Category ^a
Target lesions: iCR; non-target lesions: iCR; new lesions: no	iCR	iCR
Target lesions: iCR/iPR; non-target lesions: non-iCR/non-iUPD; new lesions: no	iPR	iPR
Target lesions: iSD; non-target lesions: non-iCR/non-iUPD; new lesions: no	iSD	iSD
Target lesions: iUPD with no change, or with a decrease from last timepoint; non-target lesions: iUPD with no change, or decrease from last timepoint; new lesions: yes	Not applicable	New lesions confirm iCPD if new lesions were previously identified and have increased in size (≥ 5 mm in sum of measures for new lesion target or any increase for new lesion non-target) or number; if no change is seen in new lesions (size or number) from last timepoint, assignment remains iUPD
Target lesions: iSD, iPR, iCR; non-target lesions: iUPD; new lesions: no	iUPD	Remains iUPD unless iCPD is confirmed on the basis of a further increase in size of non-target disease (does not need to meet RECIST 1.1 criteria for unequivocal progression)
Target lesions: iUPD; non-target lesions: non-iCR/non-iUPD, or iCR; new lesions: no	iUPD	Remains iUPD unless iCPD is confirmed on the basis of a further increase in sum of measures ≥ 5 mm; otherwise, assignment remains iUPD.
Target lesions: iUPD; non-target lesions: iUPD; new lesions: no	iUPD	Remains iUPD unless iCPD is confirmed based on a further increase in previously identified target lesion iUPD in sum of measures ≥ 5 mm or non-target lesion iUPD (previous assessment need not have shown unequivocal progression)
Target lesions: iUPD; non-target lesions: iUPD; new lesions: yes	iUPD	Remains iUPD unless iCPD is confirmed on the basis of a further increase in previously identified target lesion iUPD sum of measures ≥ 5 mm, previously identified non-target lesion iUPD (does not need to be unequivocal), or an increase in the size or number of new lesions previously identified
Target lesions: non-iUPD or progression; non-target lesions: non-iUPD or progression; new target lesions: yes	iUPD	Remains iUPD unless iCPD is confirmed on the basis of an increase in the size or number of new lesions previously identified
Target, non-target, and new lesions defined according to RECIST 1.1; if no pseudoprogression occurs, RECIST 1.1 and iRECIST categories for complete response, partial response, and stable disease would be the same.		

^a“i” indicates immune responses assigned using iRECIST.
 
Abbreviations: iCPD = confirmed progression; iCR = complete response; iPR = partial response; RECIST = Response Evaluation Criteria in Solid Tumors; iSD = stable disease; iUPD = unconfirmed progression.
		

	Timepoint Response with No Previous iUPD in Any Category	Timepoint Response with Previous iUPD in Any Category^a
a Previously identified in assessment immediately before this timepoint.		

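### Appendix 2 is inconsistent on whether a first-ever new lesion after iUPD confirms progression: the narrative and comparison table allow it, the assignment table makes no provision for it

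*Protocol*

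**What the plan says.** Protocol Appendix 2 deals with confirmation of iUPD in three places.

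- **Narrative.** iUPD is confirmed at the following assessment by an "increase in size or number of lesions". It persists when neither number nor size has changed. No condition is placed on whether a new lesion was seen before.
- **Comparison of RECIST 1.1 and iRECIST, new-lesions row.** After describing confirmation by further or growing new lesions, it adds that "the appearance of new lesions when none have previously been recorded, can also confirm iCPD".
- **Assignment of Timepoint Response.** Three rows have new lesions present.
  - The first (target and non-target iUPD, each unchanged or smaller) says "New lesions confirm iCPD if new lesions were previously identified and have increased in size" beyond a threshold, or in number. It also says "if no change is seen in new lesions (size or number) from last timepoint, assignment remains iUPD".
  - The second (target iUPD, non-target iUPD) keeps iUPD unless targets grow by at least 5 mm, non-target disease increases, "or an increase in the size or number of new lesions previously identified".
  - The last row reads "Remains iUPD unless iCPD is confirmed on the basis of an increase in the size or number of new lesions previously identified".

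The iPFS rule in the same appendix dates the event at iUPD, "provided that iCPD is confirmed at the next assessment". The narrative adds: "The assessment of iUPD can be made multiple times".

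**The concern.** Worsening in the target lesions followed by a first new lesion is an ordinary way for melanoma to progress, so the rules should give it one answer. As written, a site scoring from the assignment table and a programmer working from the narrative can classify the same scan differently. Response is assessed by investigators at up to 20 sites, so this becomes a source of between-site variation.

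At stake are the timing, and sometimes the occurrence, of an iPFS event. A patient left at iUPD also stays open, under the assignment table, to a later immune response. Both effects would flatter the iRECIST results. An event rule still unsettled at database lock would have to be chosen with the data of an open-label study in view.

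**Working it through.** No figure in the plan is at issue. The check is to classify one constructed patient under each rule.

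**Inputs.** The Appendix 2 rules set out above, and the scan schedule in Protocol 10.3.1: nine-weekly for six months, then three-monthly.

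**Patient.** Week 9: target and non-target lesions are iUPD, with no new lesions. Week 18: both are still iUPD and unchanged in size, with one new lesion, the first ever seen. This assumes that the patient is still being scanned at Week 18, although Week 9 is already PD under RECIST 1.1.

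**Classification of the Week 18 scan.**

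1. *Narrative.* New lesions go from 0 to 1, so lesion number has increased and iUPD is confirmed. The condition for repeating iUPD (no change in number or size) is not met. Result: iCPD.
2. *Comparison table.* No new lesions were on record and one has appeared. It can confirm iCPD.
3. *iPFS rule applied to 1 and 2.* The Week 9 iUPD is confirmed at the next assessment, so the event is dated Week 9: 9 × 7 / 30.44 = 2.1 months.
4. *Assignment table, target and non-target iUPD with new lesions.* Target growth of at least 5 mm: no. Non-target increase: no. Increase in new lesions already identified: there were none. No listed trigger is met. Result: still iUPD, with no iPFS event at this assessment.
5. *Assignment table, first new-lesion row.* The patient fits this description too. The confirming branch needs lesions already identified, which fails. The branch that keeps iUPD needs no change in number, and 0 to 1 is a change. Result: no outcome assigned.
6. *Assignment table, last row.* It describes a different target and non-target status but carries the same restriction as item 4.

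**What happens next under the assignment table.** If a later scan shows further growth, iCPD is reached then. If there is no later scan, it is never reached. The documents do not settle whether there will be one. Protocol 10.3.1 continues scans until confirmed PD. Section 6.2 and footnote b of the Schedule of Assessments describe post-treatment disease assessment for patients who stop for reasons other than PD.

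**Event date after consecutive iUPDs.** Suppose iUPD at Week 9, iUPD at Week 18 and iCPD at the following scan. The rule's opening gives the first date on which progression criteria were met, Week 9. Its proviso, taken literally, is satisfied only by the Week 18 iUPD. The two readings differ by 18 − 9 = 9 weeks, again 2.1 months. The next sentence of the rule sets aside only an iUPD followed by iSD, iPR or iCR. That did not happen here, so Week 9 is the more natural reading.

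**Reach.** SAP 1.3.1, 1.3.2, 4.2.1 and Table 4-1 tie ORR, PFS, CRR, DOR and DCR to RECIST 1.1, under which any new lesion is PD (Appendix 1). iORR and iPFS appear in the SAP abbreviations, and Table 4-3 on iPFS is listed in its contents. The body of that table is not in the public text.

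**The case against.** The best reply is that Appendix 2 already settles the case. The narrative and comparison table agree, the assignment table is introduced only as guidance, and the best-overall-response paragraph treats progression at the assessment after iUPD as meeting the iCPD criteria. On this view a careful reader reaches iCPD and the assignment table is merely incomplete. This stands for the first new-lesion row, which is silent. It does not stand for the other two. They are worded as closed rules: the patient stays at iUPD unless a listed trigger occurs, and a first-ever new lesion is not listed. A site following them as written gets a different answer.

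A second reply is that the comparison table says only that such lesions can confirm, and that the patient may be confirmed at a later scan. Both are true. The assignment table still offers no route to use that permission, and the later scan is not assured.

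A third is that the endpoint is redacted in the protocol and SAP Table 4-3 cannot be seen, so the analysis may already fix the event date. That is fair, and nothing is claimed here about that table. The inconsistency lies in the visible scoring rules that feed it.

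**Conclusion.** The inconsistency is real and can be checked within Appendix 2. For the constructed patient it is the difference between iCPD with an iPFS event dated Week 9 and iUPD with no event at the Week 18 assessment. It is a minor point, confined to iPFS and iORR.

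A reader might infer more than the documents support:

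- *That all three rows state the opposite of the comparison table.* Two do; the first new-lesion row leaves the case unclassified.
- *That target growth alone followed by a new lesion shows the conflict.* That patient fits no assignment row cleanly. The firm example needs non-target iUPD as well.
- *That a set share of patients turns from event to non-event.* Assuming that 10% to 30% of an arm of 20 follows this path gives 2 to 6 patients. The documents give no basis for that share, and the count also assumes that none is confirmed later.
- *That such patients would be credited with later immune responses.* The assignment table leaves this open, but the best-overall-response paragraph points the other way.
- *That the iPFS date rule contradicts itself.* It is a partial ambiguity, largely resolved by its own next sentence.

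**What to change.** In each of the three new-lesion rows of the assignment table, keep the existing target, non-target and new-lesion size criteria and add: *or new lesions appear for the first time after iUPD in another category*. The clause must be added to the row and must not replace it. Replacing the row would delete the 5 mm target criterion, the non-target criterion and the new-lesion size threshold, and would create new conflicts with the comparison table.

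In the iPFS rule, add: *for consecutive iUPDs ending in iCPD with no intervening iSD, iPR or iCR, the event date is the first iUPD of that run*. Then check that SAP Table 4-3 uses the same rule.

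The cost is wording in the appendix and, if needed, the SAP, best settled before database lock. Some events will be recognised earlier, so iPFS may come out slightly shorter. The primary and secondary analyses do not change.
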